14.5.2 The CTR responsibilities

Following the initial report, all SAEs should be followed up to resolution wherever possible, and further information may be requested by the CTR. Follow up information must be provided on a new SAE form.

The CTR should continue reporting SAEs until 30 days after the participant receives their last dose of the investigational medicinal product. Serious adverse reactions should continue to be reported until the end of follow up.

Once an SAE is received at the CTR, it will be evaluated by staff at the CTR and sent to the Chief Investigator (or their delegate) for an assessment of expectedness.

Investigator reports of suspected SARs will be reviewed immediately and those that are identified as SUSARs are reported to the sponsor, IMP supply company, MHRA and REC.

14.6 SUSAR reporting

CAVUHB is undertaking the duties of trial Sponsor and has delegated to the CTR the responsibility for reporting SUSARs and other SARs to the regulatory authorities (NCAs and relevant ethics committees).

- SUSARs which are fatal or life-threatening must be reported to the MHRA and REC within 7 calendar days of receipt at the CTR.
- SUSARs that are not fatal or life-threatening must be reported to the MHRA and REC within 15 days
 of receipt at the CTR.

If report is incomplete then additional follow-up information should be reported within a further 8 calendar days of submitting the initial report, for all fatal and non-fatal, life-threatening and non-life-threatening

Any additional, relevant information must be reported within a further 15 days.

14.7 Unblinding for the purposes of SUSAR reporting

To enable processing of a SAR in this blinded trial, expectedness should be assessed initially using the assumption that the IMP has been given to the trial participant.

If it is assessed as unexpected as per the RSI of the IMP, the SUSAR will be unblinded by the CTR safety group prior to reporting to any onward reporting.

If after unblinding it is evident that the trial participant received the placebo, this event will not require expedited reporting to the NCAs and REC, unless in the opinion of the Principal Investigator or Chief Investigator the event was related to the placebo (for example an allergic reaction to an excipient).

14.8 Safety Reports

A list of all SARs (expected and unexpected) will be reported annually to the MHRA REC and trial sponsor in the form of a Development Safety Update Report (DSUR). This report must be submitted within 60 days of the anniversary of the MHRA CTA approval date.

The CTR will report a list of all SARs (expected and unexpected) and any other safety recommendations to all PIs throughout the course of the trial. This frequency may be reviewed and amended as necessary. This reporting will be done via the Investigator safety report (ISR).

14.9 Pregnancy

14.9.1 Pregnancy reporting whilst participating in the trial

Flucloxacillin is not known to cause congenital anomalies or birth defects and is considered generally safe in pregnancy. Information on a pregnancy in a trial participant will be captured on the Trial CRF pre surgery. No further pregnancy data will be recorded.

14.10 Urgent Safety Measures (USMs)

An urgent safety measure is an action that the Sponsor, Chief Investigator or Principal Investigator may carry out in order to protect the subjects of a trial against any immediate hazard to their health or safety. Any urgent safety measure relating to this trial must be notified to the MHRA and Research Ethics Committee immediately by telephone, and in any event within 3 days in writing, that such a measure has been taken. USMs reported to the CTR will be handled according to CTR processes.

15 Statistical considerations

15.1 Randomisation

The randomisation procedure will be implemented via a web-based remote system (available 24 hours a day) as described in Section 9.5.2. Randomisation will occur prior to surgery. Allocations minimised (with random element) by SSI risk associated with reconstruction method (primary closure, skin graft or local skin flap) and anatomical site (below knee or other anatomical site) and stratified by the recruitment site. Full details will be provided in a separate randomisation protocol.

15.2 Blinding

Participants, clinicians and outcome assessors will be blinded to the randomised allocation. Further details will be included in the trial Unblinding plan.

15.3 Sample size

We will randomise 380 participants between the two groups (190 participants per group) with a 1:1 allocation ratio. This is based on a two-sided alpha of 0.05, 90% power, an assumed SSI rate of 30% for those allocated to placebo, a target effect size of 15% (absolute risk difference) and is inflated for 15% loss to follow-up.

We will conduct a futility analysis after 165 participants provide analysable outcome data (based on our assumed 15% drop-out rate, we anticipate this being after randomising 196 participants and following them up to the primary endpoint timepoint). Using an O'Brien-Fleming boundary, our critical threshold to indicate futility will be z = 0.27 (equivalent to an absolute risk difference of 2% or a one-sided p-value of 0.39). To maintain an overall alpha of 0.05 (two-sided), the maximum sample size will be 390 participants (a 3% increase on the target sample size with a fixed design).

For varying event rates, the Table 7 below demonstrates the futility threshold and corresponding effect size and one-sided p-value, based on an interim analysis after 165 participants have analysable data. For example, if the event rate in the placebo arm is 20%, our critical threshold to indicate futility will be z = 1.39 and our maximum sample size will be 256 participants. Where the event rate is greater than 30% and the maximum sample size is larger than what we have planned, we would approach the HTA Programme for a view on further funding to recruit from a larger number of sites and calculate participant costs accordingly. We will do this without impacting on overall timelines as this will be efficient given that it will not require an increase in staff time.

Our futility boundary will be non-binding, and our DMEC will be asked to consider their decision within the context of other data (e.g. secondary outcomes, safety data, etc.) (as described in the table 7 below).

Table 7. - Futility boundary

Event rate	Futility threshold*	Effect size**	One-sided p- value	Maximum sample size***
20%	1.39	7	0.08	256
25%	0.71	4	0.24	328
30%	0.27	2	0.39	390
35%	-0.06	0	0.52	444
40%	-0.28	-2	0.61	486

^{*}Based on O'Brien-Fleming boundary. **Absolute risk difference. ***Including 15% drop-out inflation.

15.4 Missing, unused & spurious data

Further detail provided in the Statistical Analysis Plan (SAP).

15.5 Procedures for reporting deviation(s) from the original SAP

These will be submitted as substantial amendments where applicable and recorded in subsequent versions of the protocol and SAP.

15.6 Termination of the trial

Progression criteria for the internal pilot phase will be described. There is the potential for the trial to terminate early if our funder assesses the trial as not being feasible following the assessment of progress against our targets at the end of the internal pilot with input from our TSC and IDMC.

15.7 Inclusion in analysis

This analysis will include all randomised participants regardless of intervention receipt (as we will be using a treatment policy strategy for handling this intercurrent events).

16 Analysis

16.1 Main analysis

Descriptive statistics will be summarised using frequencies and percentages, means and standard deviations, or medians and interquartile ranges, as appropriate. A comprehensive Statistical Analysis Plan will be approved by the Trial Steering Committee and Trial Data Monitoring Committee prior to database lock and commencement of analysis. The findings will be reported according to the Consolidated Standards of Reporting Trials (CONSORT) statement. We will incorporate the estimand framework within our protocol and

statistical analysis plan (57), with the aim of specifying primary and sensitivity estimands and aligning analysis strategies accordingly.

For the primary outcome statistical analysis, we will compare the proportion of participants in each arm who experience an SSI within 30 days of randomisation using logistic regression. The model will adjust for reconstruction method, anatomical site of surgery and recruitment site. This analysis will include all randomised participants regardless of intervention receipt (as we will be using a treatment policy strategy for handling this intercurrent events). We anticipate deaths occurring within the 30-day post-randomisation period being extremely rare but will handle any instances by incorporating them as a poor outcome (composite strategy). Findings will be reported as odds ratios, 95% confidence intervals, and p-values.

Secondary outcomes will be analysed similarly, with linear, Poisson (or negative binomial), and flexible parametric survival models fitted as appropriate.

Missing data and non-adherence patterns will be described. We will explore their extent and mechanisms and apply appropriate statistical methods for handling these (e.g., multiple imputation, complete case analysis, inverse probability of treatment weighting). Adherence patterns will be characterised using the ABC taxonomy (58). Furthermore, when developing the trial protocol, we will use the estimand framework to outline strategies for handling intercurrent events.

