5.4 Primary outcomes measure

To compare the proportion of participants in the oral flucloxacillin group with the no antibiotic (placebo) group diagnosed with Surgical Site Infection within 30 days post-randomisation.

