The EQ-5D 5L will be used to derive health utilities to inform the calculation of Quality Adjusted Life Years as the preferred measure by NICE to capture HRQOL in adults for use in a cost-utility analysis (CUA). With the lack of any validated PROM to capture utilities lost/ gained related to a skin-cancer specific SSI, the EQ-5D has been used in other SSI trials in the UK and is described in a recent handbook that has documented utility based QoL measures in melanoma populations (64). The most appropriate method at the time of analysis to derive utilities for a UK population (e.g. pending completion of the on-going UK EQ-5D 5L valuation exercise (Euroqol) in 2024 or using the recognised cross-walk function to the 3L version (65-67). The primary clinical outcome

measure will be used in a cost-effectiveness analysis. For the primary analyses, no discounting will be undertaken as the horizon will be <12 months.

Adjusted analyses using suitable regression models will be conducted. Missing data will be examined and accounted for by suitable measures e.g., multiple imputation for missing observations of costs and utilities, following Rubin's rules. Imputed data will be used within our base-case analysis with complete case analysis used as a sensitivity analysis. Analysis based on the ITT trial population to calculate the incremental cost per QALY at 3 months with calculation of incremental net monetary benefit (iNMB), presented across different cost-effectiveness thresholds. A cost-effectiveness analysis (CEA) will present the incremental cost per SSI prevented at 30 days, as part of a complementary set of analyses and to reflect other comparable CEAs in the field (68). Deterministic sensitivity analyses will examine the impact of uncertainty in our findings e.g., changing parameters, alongside the supplementary analysis to include patient costs, and appropriate subgroup analyses (e.g., anatomical site). For the CUA, bootstrapping will be undertaken to assess joint uncertainty. A cost-effectiveness acceptability curve will present the probability that either one of the techniques is cost-effective, based on the commonly used NICE willingness to pay threshold of £20-30,000 per QALY gain.

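### Section 16.1 names only an adjusted odds ratio for the primary result, while the target effect is a 15-point absolute risk difference; add the adjusted risk difference with its interval

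*Protocol*

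**What the plan says.** - **Target (Protocol 15.3).** The sample size assumes "an assumed SSI rate of 30% for those allocated to placebo" and "a target effect size of 15% (absolute risk difference) and is inflated for 15% loss to follow-up". Table 7 lists an effect size for each event rate, footnoted as an absolute risk difference.
- **Outcome (Protocol 5.4).** The primary outcome is stated as a contrast of proportions: "To compare the proportion of participants in the oral flucloxacillin group with the no antibiotic (placebo) group".
- **Analysis (Protocol 16.1).** The proportions with SSI within 30 days are compared by logistic regression adjusted for reconstruction method, anatomical site and recruitment site. On the result it says: "Findings will be reported as odds ratios, 95% confidence intervals, and p-values". The section also promises descriptive frequencies and percentages, CONSORT reporting, and use of the estimand framework in both Protocol and SAP. It names no risk difference, risk ratio or standardisation step for the primary outcome.
- **Economics (Protocol 16.2).** The main result is cost per QALY at 3 months. A complementary analysis gives the "incremental cost per SSI prevented at 30 days".

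**The concern.** The trial asks whether one dose lowers SSI risk by an amount worth having, and expresses that amount in percentage points. The one effect measure that the analysis section commits to is on another scale. An odds ratio corresponds to a different absolute benefit at each placebo rate, and section 15.3 itself allows for rates from 20% to 40%. The adjusted odds ratio is also conditional on the covariates, so in general it differs from the odds ratio formed from the two overall proportions that section 5.4 compares.

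At stake is the adjusted interval on the scale of the target. Without it, a reader cannot see directly how many SSIs per 100 treated patients the data support, or whether the interval includes 15 points. The Protocol does not commit to producing it.

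**Working it through.** **Inputs.** All are from Protocol 15.3 unless marked: two-sided alpha 0.05; power 90%; placebo rate 30%; target difference 15 points, so 15% on flucloxacillin; 15% loss; 380 randomised 1:1; 165 analysable at the interim; Table 7 z thresholds.

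**1. The plan's own sample size.** With pooled variance under the null and no continuity correction, n per arm = [1.96√(2 × 0.225 × 0.775) + 1.2816√(0.30 × 0.70 + 0.15 × 0.85)]² / 0.15² = 161 after rounding up. Inflated for loss, 161/0.85 = 189.4, or 190 per arm and 380 in total. The stated figure reproduces.

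**2. The scale of Table 7.** Effect size = z × SE of the risk difference with 82.5 per arm. At 30%: 0.27 × √[(0.30 × 0.70 + 0.15 × 0.85)/82.5] = 0.27 × 0.0640 = 1.7 points. All rows:

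| Placebo rate | z | Recomputed (points) | Table 7 |
|---|---|---|---|
| 20% | 1.39 | 7.0 | 7 |
| 25% | 0.71 | 4.1 | 4 |
| 30% | 0.27 | 1.7 | 2 |
| 35% | -0.06 | -0.4 | 0 |
| 40% | -0.28 | -2.0 | -2 |

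The table was worked on the risk-difference scale.

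**3. What the odds ratio says about the target.** Design OR = (0.15/0.85)/(0.30/0.70) = 0.412. At placebo rate p the treated odds are 0.412 × p/(1 - p). At 20% these are 0.412 × 0.25 = 0.103, a risk of 9.3% and a difference of 10.7 points. At 40% they are 0.412 × 0.667 = 0.275, a risk of 21.5% and a difference of 18.5 points. The reverse calculation fixes the difference at 15 points; at 20%, for example, OR = (0.05/0.95)/(0.20/0.80) = 0.21.

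| Placebo rate | Difference if OR = 0.412 | OR if difference = 15 points |
|---|---|---|
| 20% | 10.7 | 0.21 |
| 25% | 12.9 | 0.33 |
| 30% | 15.0 | 0.41 |
| 35% | 16.9 | 0.46 |
| 40% | 18.5 | 0.50 |

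**4. Conditional and marginal odds ratios.** The Protocol gives no figure for how strongly the covariates predict SSI, so this step is an assumption shown as a range. If they spread the logit normally with SD 0.5, 1.0 or 1.5, overall risks of 30% v 15% correspond to a conditional OR of 0.40, 0.36 or 0.31, against the marginal 0.41.

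**5. Effect on inference.** With 380 × 0.85 = 323 analysable (161.5 per arm) and true rates of 30% v 15%, unadjusted:
- Log odds: SE = √(1/48.45 + 1/113.05 + 1/24.225 + 1/137.275) = 0.279; z = 0.887/0.279 = 3.18; Wald power about 0.89.
- Risk difference: SE = √(0.3375/161.5) = 0.0457; z = 0.15/0.0457 = 3.28; Wald power about 0.91.

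Both are within 2 points of the planned 90%. The expected 95% interval for the risk difference is 15 ± 9.0, about 6 to 24 points.

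**The case against.** The strongest case on the other side is that an adjusted odds ratio, from a logistic model containing the minimisation and stratification factors, is a legitimate primary measure. Assuming 30% v 15% fixes two proportions and so specifies OR 0.41 just as much as 15 points. The sentence in 16.1 excludes nothing, arm percentages are promised, the placebo rate will be observed, and the SAP, which is not at hand, may add other measures. All of this stands. It rules out replacing the odds ratio as anything more than a preference. It does not supply an adjusted absolute difference with an interval: arm percentages give only a crude contrast, and the Protocol commits to nothing further.

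A reader might infer several stronger things that the documents do not support:

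- **That futility is monitored on the risk difference.** The rule in 15.3 is a z threshold, with the 2-point difference given as an equivalent. Under 16.1.1 the interim uses the same logistic model as the final analysis, so the two agree.
- **That the economic evaluation depends on the risk difference as a whole.** Only the complementary cost-per-SSI analysis does. The evaluation has its own analysis plan and regression models, and nothing says it will take the clinical odds ratio as input.
- **That no risk difference will be produced.** The Protocol names none, which is not the same as excluding one.
- **That the plan overstates benefit.** At 30% v 15%, the odds ratio suggests a 59% reduction instead of 50% only if it is misread as a risk ratio.

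**Conclusion.** The point holds as a gap in the reported effect measure. The target, the Table 7 effect sizes and the cost per SSI prevented are on the absolute scale, and the only measure section 16.1 names for the primary outcome is an adjusted odds ratio. Over the Protocol's own range of placebo rates, the design odds ratio spans 10.7 to 18.5 points, so it cannot be set against the 15-point target without the placebo rate. That span is plain arithmetic on the Protocol's figures. The further shift from conditioning on covariates (0.40 to 0.31 against 0.41) rests on assumed covariate strength and is only indicative.

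The sample size reproduces, and power is about the same on either scale. It would be wrong to conclude that the hypothesis test is invalid or the trial underpowered. The fitted model already contains what is needed to estimate the absolute difference. This is a cheap improvement, worth making before database lock.

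**What to change.** In Protocol 16.1, and in the SAP to match:

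- Keep the adjusted odds ratio with its 95% confidence interval and p-value.
- Add the adjusted absolute risk difference, and preferably the risk ratio, each with a 95% confidence interval. Obtain them by standardisation: predict each participant's SSI risk from the same logistic model under each allocation, average over all participants, and contrast the averages.
- Give the number and percentage with SSI in each arm beside these estimates.
- State which measure is the population-level summary of the primary estimand.

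Using the same risk difference in the cost per SSI prevented would keep the clinical and economic reports consistent. The cost is a few lines of analysis code and a wording amendment. The sample size, data collection and futility rule need no change.

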16.1.1 Sub-group & interim analysis

Exploratory subgroup analyses will be hypothesis-generating in nature and be used to study the extent to which the proportions may differ for our primary outcome across the following subgroups:

- Reconstruction method (primary closure, skin graft, local skin flap);
- Anatomical site (below knee, other anatomical site);
- Specialty recruiting the participant (dermatology, other specialities (including plastic surgery, ear, nose and throat surgery and maxillofacial);
- Surgical setting (procedure room, theatre);
- Suture type used (antimicrobial coated sutures, non-antimicrobial sutures

IRAS: 1009425

We will conduct an interim futility analysis after 165 participants provide analysable outcome data (based on our assumed 15% drop-out rate, we anticipate this being after randomising 196 participants and following them up to the primary endpoint timepoint). This analysis will be the same model as the primary analysis: a logistic regression model to compare the proportion of participants in each arm who experience an SSI within 30 days of randomisation adjusted for reconstruction method and anatomical site of surgery and recruitment site. Detail of all interim analyses is available in the EXCISE Interim Statistical Analysis Plan.

16.2 Cost effectiveness analysis

With the potential for SSI's increasing use of health care resources (59) alongside the impact on quality of life (12) whilst considering the economic impact of antibiotic stewardship programmes (60), a health economic evaluation as part of the EXCISE trial will be conducted to assess the cost- effectiveness of a single pre operative dose of oral flucloxacillin and standard care compared to no antibiotic and standard care for ulcerated skin cancers. The evaluation will be designed, conducted and reported following best-practice guidelines (61), with a Health Economic Analysis Plan (HEAP) produced as part of a comprehensive SAP as detailed earlier. A UK NHS/ Personal Social Services Perspective will be taken for the base-case (primary) analysis. Discussions with the EXCISE research team and patient representatives during the development of the EXCISE grant submission highlighted the impact of managing SSIs to the patient and society, thus an additional (restricted) societal perspective to collect additional costs (e.g., out of pocket expenses) alongside time away from usual activities (e.g., loss of workdays) will be included as supplementary analysis. Economic outcomes will be collected as part of the EXCISE data collection schedule, described earlier.

Resource use data associated with the primary surgical procedure (e.g., length of visit/stay) and antibiotic use will be gathered via the trial case report forms. Subsequent health and care resource use data related to wound complications, including SSI, will be collected, alongside key personal costs and lost workdays. The resource use data collection measure/schedule will be developed in collaboration with the EXCISE research team and patient representatives, drawing upon good practice to balance the requirement for comprehensive information against the burden (both participant and researcher) of completion (62,63). The internal pilot phase will assess the collection of economic outcome measures and inform the first iteration of the HEAP. Published UK unit costs will be used to value resource use in £ sterling to the most relevant price year available at time of final analysis. Total and per participant costs will be presented based on the available case dataset to provide a comprehensive summary of the resource use and costs associated with the intervention and comparator groups over the trial period.

The EQ-5D 5L will be used to derive health utilities to inform the calculation of Quality Adjusted Life Years as the preferred measure by NICE to capture HRQOL in adults for use in a cost-utility analysis (CUA). With the lack of any validated PROM to capture utilities lost/ gained related to a skin-cancer specific SSI, the EQ-5D has been used in other SSI trials in the UK and is described in a recent handbook that has documented utility based QoL measures in melanoma populations (64). The most appropriate method at the time of analysis to derive utilities for a UK population (e.g. pending completion of the on-going UK EQ-5D 5L valuation exercise (Euroqol) in 2024 or using the recognised cross-walk function to the 3L version (65-67). The primary clinical outcome

measure will be used in a cost-effectiveness analysis. For the primary analyses, no discounting will be undertaken as the horizon will be <12 months.

Adjusted analyses using suitable regression models will be conducted. Missing data will be examined and accounted for by suitable measures e.g., multiple imputation for missing observations of costs and utilities, following Rubin's rules. Imputed data will be used within our base-case analysis with complete case analysis used as a sensitivity analysis. Analysis based on the ITT trial population to calculate the incremental cost per QALY at 3 months with calculation of incremental net monetary benefit (iNMB), presented across different cost-effectiveness thresholds. A cost-effectiveness analysis (CEA) will present the incremental cost per SSI prevented at 30 days, as part of a complementary set of analyses and to reflect other comparable CEAs in the field (68). Deterministic sensitivity analyses will examine the impact of uncertainty in our findings e.g., changing parameters, alongside the supplementary analysis to include patient costs, and appropriate subgroup analyses (e.g., anatomical site). For the CUA, bootstrapping will be undertaken to assess joint uncertainty. A cost-effectiveness acceptability curve will present the probability that either one of the techniques is cost-effective, based on the commonly used NICE willingness to pay threshold of £20-30,000 per QALY gain.

With the restricted trial horizon, in addition, the aim will be to explore longer-term cost-effectiveness, from a UK NHS/ PSS perspective, through building a decision analytic model. The rationale for this consideration is that clinical and patient representatives have expressed potential for longer term impact on HRQOL, particularly given the differences could be small within the EXCISE horizon. Appropriate caution will be taken in planning this exploratory analysis to ensure any extrapolation would be useful, feasible and plausible as part of presenting a comprehensive picture of cost-effectiveness. Initial discussions with the EXCISE team and patient representative suggest a 1-year time horizon would be plausible to capture any potential longer-term costs and consequences of an SSI related to the initial surgery. Evidence from EXCISE will be key to inform parameters. If the time horizon goes beyond 1 year, discounting will be applied for costs and effects (3.5%). A rapid literature review will be undertaken to identify data inputs (e.g., longer-term utility estimates associated with an SSI (69), alongside clinical opinion to supplement EXCISE data. The model will be built in MS Excel, with the model structure, inputs and assumptions agreed with the EXCISE team and clinicians, prior to analysis. A CUA based on the agreed time horizon(s) will be presented, similar to the primary analysis, presented above. Uncertainty in the parameters used to populate the model will be examined through deterministic sensitivity analysis, with joint uncertainty explored using probabilistic sensitivity analysis.

